8.7.1. Statistical analysis plan

- 1. Among each medication use group, a report with descriptive statistics of the demographic and clinical baseline characteristics as well as medication use prior to rimegepant will be created.
- 2. Next, a patient-level dataset containing crude counts of the five utilization outcome measures for each 30-day window (W1-W12) of the pre- and post-index periods will be created.
- 3. To measure changes in utilization outcome measures across the pre-index to post-index period, two aggregated measures for each outcome based on time during the pre- (W1-W6) or post-index (W7-W12) period will be created. Using these aggregate measures, the pre and post-index mean outcome values and determine the percent change (%Δ) will be presented.
- 4. In order to determine the association between rimegepant initiation and reduction of other acute treatments, a generalized linear mixed models for each outcome will be applied. Mixed effects models account for within-person correlation due to the repeated measurement of outcomes over time in longitudinal studies. The main independent (exposure) variable will be a binary indicator of time during the pre-index period (0) vs. post-index period (1). For modeling the continuous and count outcomes—number of fills, quantity dispensed, average dose, and duration of use—first the distribution of each utilization outcome measure within the dataset will be determined in order to specify the appropriate distributions and link functions for their mixed model. The discontinuation outcome is a binary outcome, observed at one point in time. Hence, a logistic regression model to examine any association to rimegepant initiation will be applied. For each model, for pre-index demographic and clinical characteristics, including age, sex, region, presence of any chronic pain (migraine or non-migraine), Elixhauser weighted index, and pre-index use of any prevention agent will be adjusted.
- 5. To determine the robustness of the outcome measures and association estimates, two subgroups and two sensitivity analyses will be performed as described below. The sensitivity analyses only apply to the total cohort, and not the additional subgroups.
 - a) Subgroup analysis #1: Identify all individuals from the total cohort with use of ≥ 1 prevention agent during the pre-index period, presented by medication use group.

- b) Subgroup analysis #2: Identify individuals form the opioid use group having potentially problematic opioid use. This subgroup is a composite of problematic opioid use defined in two ways. Patients meeting either measurement definition will be included.
 - i. The first method will identify individuals in the cohort with ≥ 3 opioid prescriptions during the pre-index period.
- 6. The second method will calculate quartiles of opioid dose in MMEs and identifies individuals within the fourth quartile (76th to 100th percentile) during the pre-index period.
 - c) Sensitivity analysis #1: Increase the duration of the pre-index and post-index periods from 180 days each to 360 days each.
 - d) Sensitivity analysis #2: Exclude all patients having a major surgical procedure or injury diagnosis at any point during the study period.

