Variables: The primary exposure is initiation of rimegepant, defined by the first prescription fill between March 1, 2020, and October 1, 2022. Outcomes include changes in opioid and barbiturate utilization patterns before and after rimegepant initiation, measured by prescription fills, quantity dispensed, average dose, duration of use, and discontinuation. Key covariates are demographic and clinical characteristics (age, sex, region, comorbidities, chronic pain, prior preventive treatments) assessed during the baseline period.

Data sources: This study will analyze the IQVIA PharMetrics[®] Plus longitudinal health plan database, which includes anonymized, medical and pharmacy claims from closed-network, third-party payers in the US. This database includes commercial, managed Medicare, and managed Medicaid health plans.

Study size: The study database includes 52,591,063 individuals. It is estimated that 45,051 (0.86%) have an eligible first prescription for rimegepant and 4,049 (0.0077%) meet all eligibility criteria.

Data analysis: Number of fills and quantity dispensed (in MMEs for opioids and milligrams for barbiturates) will be assessed in the 180 days before and after the index fill for rimegepant. Changes in key outcomes will be analyzed using generalized linear mixed models adjusted for age, sex, region, chronic pain, comorbidities, and use of preventive treatment for migraine. Subgroup analyses will be conducted among individuals using ≥ 1 preventive treatment and individuals with problematic opioid use (≥ 3 fills or MMEs above 75th percentile).

Milestones: This study was initiated in 2023. Analyses were completed in 2024. A manuscript based on this study was accepted for publication in 2025.

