8.2.1. Inclusion Criteria

Patients must meet all of the following inclusion criteria to be eligible for inclusion in the study:

- 1. Have an index ("first") prescription fill for rimegepant between March 1, 2020, and October 1, 2022; the date of this index fill defines the index date
 - a. The end date of cohort eligibility is 6 months prior to the end of data availability to ensure sufficient follow-up for all patients prior to the end of data availability. For the 12-month sensitivity analysis, the end of cohort eligibility will be April 1, 2022.
- 2. Have an index fill quantity for rimegepant of 8 tablets (ie, intended use for acute treatment of migraine).
- 3. Have ≥ 180 days of rimegepant use from index date to last fill date +30 days
 - a. The period of rimegepant use is measured as the number of days from the index date, or first observed rimegepant fill, to the last observed rimegepant fill date +30 days.
- 4. Be \geq 18 years of age on the index date

- 5. Have ≥180 days of continuous enrollment in commercial health plans with both medical and pharmacy benefits prior to and following the index date, defined as the pre-index period and post-index period, respectively
- 6. Have a diagnosis of "migraine" (ICD-10-CM code: G43.xx) at *any point* during the pre- or post-index periodsHave ≥1 prescription fill during the pre-index period for one of the following drugs of interest: opioids, barbiturates (butalbital), alprazolam, rescue inhalers, or statins

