Any injury	Baseline characteristic	Medical claims	Binary (ICD-10)	
Any surgical procedure	Baseline characteristic	Medical claims	Binary (CPT)	
	Outcon	ne Measures		
Total number of fills dispensed	Outcome measure	Rx claims	Count	
Total quantity dispensed	Outcome measure	Rx claims	Count	
Average dose (MME or mg) within time period	Outcome measure	Calculated	Continuous (calculated): Mean/SD	
Total duration of use (days)	Outcome measure	Calculated	Continuous (calculated)	
Discontinuation	Outcome measure	Rx claims	Binary (no prescription fills during post-index period)	
Additional measures for opioid use group:				
Type of opioid used	Outcome measure	Rx claims	Binary	
Total number of Rx opioid agents used (mean)	Outcome measure	Rx claims	Count	
Total number of Rx opioid agents used	Outcome measure	Rx claims	Categorical: $1, 2, \ge 3$	

CGRP: Calcitonin Gene-Related Peptide; CPT: Current Procedural Terminology; HCPCS: Healthcare Common Procedural Coding System; ICD10: International Classification of Diseases, 10th Revision; MME: Morphine Milligram Equivalents; NSAIDs: Nonsteroidal anti-inflammatory drugs; Rx: Prescription; SD: Standard Deviation

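### Discontinuation is not adjusted or stratified by pre-index fill frequency, apart from one heavy-use opioid subgroup, so differences between drug groups and covariate odds ratios can partly reflect fill frequency and not stopping

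*Protocol*

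**What the plan says.** Protocol Table 1 (section 8.3) defines discontinuation as "Binary (no prescription fills during post-index period"). Section 8.7.1, step 4, adds: "The discontinuation outcome is a binary outcome, observed at one point in time". It goes on: "Hence, a logistic regression model to examine any association to rimegepant initiation will be applied".

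One covariate set applies to each model: "including age, sex, region, presence of any chronic pain (migraine or non-migraine), Elixhauser weighted index, and pre-index use of any prevention agent". For the mixed models the Abstract gives the same list: "adjusted for age, sex, region, chronic pain, comorbidities, and use of preventive treatment for migraine". Neither list contains pre-index fills, quantity, dose or days supplied of the study drug.

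Eligibility (section 8.2.1) asks for at least one pre-index fill of a drug of interest. Table 2 (section 8.7) reports discontinuation for opioids, barbiturates, alprazolam, rescue inhalers and statins. Section 8.1 calls the last three controls, representing continuous and episodic use, and counts on them to strengthen the findings.

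The amount of baseline use defines a stratum in one place only, subgroup analysis #2. It applies to the opioid group and takes patients in the top MME quartile, or those found by a method that will "identify individuals in the cohort with ≥ 3 opioid prescriptions during the pre-index period".

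**The concern.** In the mixed models for fills, quantity, dose and duration, the pre-index value is itself a response, so each patient's own level of use is in the model. Discontinuation has one post-index observation per patient, and baseline use appears on neither side. A patient who filled once in 180 days and one who filled monthly are treated alike, although the first is far more likely to have a fill-free 180 days with no change in behaviour.

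Two kinds of result are exposed to this. One is the side-by-side reading of discontinuation across the five drugs, whose fill patterns should differ because some are meant for continuous and some for episodic use. The other is any odds ratio for a covariate tied to fill frequency, such as chronic pain. The infrequent fillers, in whom a chance gap is commonest, are never shown separately. Outside the opioid group there is no stratification by amount of use at all.

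**Working it through.** The plan states no discontinuation rate, so there is no figure to reproduce. The check asks how far fill frequency alone can produce discontinuation.

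**Inputs from the protocol.** 180 days before and after index (section 8.2); at least one pre-index fill (section 8.2.1); outcome is zero post-index fills (Table 1).

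**Assumed, because the protocol gives no fill data.** Each patient has a rate λ per 180 days, gamma distributed with shape k (0.5 to 2) and mean m (1 to 4) before the one-fill selection. Pre- and post-index fills are independent Poisson(λ). Use does not change after index.

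**Step 1, a known rate.** P(no fill) = exp(−λ): 61%, 37%, 14%, 5% and 0.25% at λ = 0.5, 1, 2, 3 and 6.

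**Step 2, by observed pre-index fills.** Let b = k/m. Given j pre-index fills, λ is gamma with shape k + j and rate b + 1, so

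P(no post-index fill | j) = [(b + 1)/(b + 2)]^(k + j).

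For example, k = 2 and m = 4 give b = 0.5: 0.6³ = 0.216 for j = 1 and 0.6⁴ = 0.130 for j = 2.

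Overall, P0 = [b/(b + 1)]^k, P00 = [b/(b + 2)]^k, and discontinuation among those selected is (P0 − P00)/(1 − P0). The figure for three or more fills follows by subtraction.

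| k, m | Overall | 1 fill | 2 fills | ≥3 fills |
|---|---|---|---|---|
| 0.5, 1 | 31% | 46% | 28% | 10% |
| 1, 2 | 20% | 36% | 22% | 7% |
| 1, 3 | 14% | 33% | 19% | 5% |
| 2, 1 | 35% | 42% | 32% | 20% |
| 2, 4 | 8% | 22% | 13% | 3% |

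Over k = 0.5, 1, 2 and m from 1 to 4 the ranges are 22-46%, 13-32% and 3-20%.

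**Step 3, two groups differing only in fill rate (k = 2).**
- m = 1: (0.444 − 0.250)/(1 − 0.444) = 35.0%
- m = 2: (0.250 − 0.111)/(1 − 0.250) = 18.5%
- m = 3: (0.160 − 0.0625)/(1 − 0.160) = 11.6%

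The odds ratio for mean 3 against 1 is (0.116/0.884)/(0.350/0.650) = 0.24; for 3 against 2 it is 0.131/0.227 = 0.58. The same formula gives 0.74 for 2.5 against 2 and 0.88 for 2.2 against 2. The true direct effect is nil (odds ratio 1) in every case.

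**Step 4, after adding log pre-index fills (simulation).** These become about 0.39, 0.72, 0.83 and 0.92. Each moves toward 1 and none reaches it, because one observed count is a noisy measure of the underlying rate.

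**Step 5, the target named in step 4 of the plan.** With one row per patient the exposure is 1 for everyone. The design matrix of intercept, exposure and one covariate has rank 2 of 3, and adding log fills gives rank 3 of 4. With two rows per patient the pre-index outcome is 0 for all by eligibility. The fit then separates completely: the log odds ratio is 10.2, 20.2 and 27.2 at 10, 20 and 30 iterations, with standard errors 3.1, 459 and 15,213.

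**The case against.** The strongest reply is that no stated estimate is biased. The discontinuation model is meant to examine association with rimegepant initiation, and every patient initiated rimegepant. Baseline use cannot confound an exposure that does not vary. Chronic pain is only an adjustment variable, and step 4 specifies no regression across drug groups. This stands. A reader might infer that the omission confounds a rimegepant effect, or that adding the covariate would rescue one; step 5 of the working shows that neither follows. What the reply leaves untouched is the comparison across the five drugs that section 8.1 and Table 2 invite, and the covariate odds ratios the model would produce.

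Second, the sizes are assumed. This also stands. A reader might infer that baseline use is the strongest determinant of discontinuation, or that the adjusted results mainly reflect it. The protocol has no fill data to support either statement, and an odds ratio near 0.24 needs a threefold gap in mean fills.

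Third, the covariate list is introduced as non-exhaustive, prior medication use is described by group in step 1, and heavy opioid users are analysed separately. These help little. The list is confined to demographic and clinical characteristics. A baseline description is not cross-classified with discontinuation. The subgroup covers one drug and isolates frequent or high-dose users, not infrequent fillers. The data dictionary and table shells in Annex 1 are not at hand and might already contain such a breakdown.

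**Conclusion.** The point holds in a limited form. Discontinuation as defined is likely to depend strongly on pre-index fill frequency, and the plan takes account of that only through the heavy-use opioid subgroup. With no change in use at all, groups differing only in mean fills can show 35% against 12% (means 1 and 3) or 19% against 12% (means 2 and 3). The direction rests only on fill rates being stable within patients and different between groups. The size rests on the assumed gamma-Poisson model and on the assumed gap, and shrinks to an odds ratio near 0.9 when the gap is small.

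It is an interpretive weakness in one of five outcomes and does not touch the mixed-model analyses. The absence of any exposure contrast in the discontinuation model is a separate limit that this point neither causes nor cures.

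**What to change.** In section 8.7.1, step 4, and Table 2:

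- Report discontinuation as a proportion with 95% CI by pre-index fill count of the group's drug (1, 2, 3 or more) in all five medication groups.
- Add pre-index fills of that drug to any discontinuation regression that compares patients or drug groups.
- State that this reduces but does not remove the dependence on baseline use.
- State that it does not make an association with rimegepant initiation estimable, since every patient initiated rimegepant and had at least one pre-index fill.

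The cost is a few sentences and some table rows: pre-index fill counts are already in the dataset built in steps 2 and 3. Some strata will be small, with an estimated 4,049 eligible patients spread over five groups. As the Abstract says analyses were completed in 2024, the breakdown would go into the final study report, labelled as an addition.

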8.2.2. Exclusion Criteria

Patients meeting any of the following criteria will be excluded from the study:

- 1. Prior use of other novel agents for acute treatment of migraine (i.e., ubrogepant or lasmiditan) in the pre-index period
- 2. Diagnosis of malignant neoplasm (cancer) during the pre or post-index periods

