8.3. Variables

The study variables and its operational definition are listed in Table 1.

Table 1. Variables description

Variable	Role	Data source(s)	Operational definition			
	Demographic characteristics					
Age	Baseline characteristic	Enrollment files	Continuous: Mean/SD			
Age categories	Baseline characteristic	Calculated	Categorical: 18-34, 35-54, 55-64, 65+			
Age 55 category	Baseline characteristic	Calculated	Categorical: 18-54, 55+			
Sex	Baseline characteristic	Enrollment files	Categorical: Male, Female, Unknown			
Region	Baseline characteristic	Enrollment files	Categorical: Northeast, South, West, Midwest			
I	Prior migraine treatm	ents during pre-index	period			
Triptans	Baseline characteristic	Rx claims	Binary (any use)			
Ergotamines	Baseline characteristic	Rx claims	Binary (any use)			
NSAIDs	Baseline characteristic	Rx claims	Binary (any use)			
Acetaminophen	Baseline characteristic	Rx claims	Binary (any use)			

		1	T
Beta blockers	Baseline characteristic	Rx claims	Binary (any use)
Tricyclic antidepressants	Baseline characteristic	Rx claims	Binary (any use)
Antidepressants	Baseline characteristic	Rx claims	Binary (any use)
Anticonvulsants	Baseline characteristic	Rx claims	Binary (any use)
Anti-CGRP monoclonal antibodies	Baseline characteristic	Rx and medical (HCPCS) claims	Binary (any use)
Onabotulinumtoxin A	Baseline characteristic	Rx and medical (HCPCS) claims	Binary (any use)
Isometheptene combinations	Baseline characteristic	Rx claims	Binary (any use)
Antiemetics (migraine)	Baseline characteristic	Rx claims	Binary (any use)
Antiemetics (other)	Baseline characteristic	Rx claims	Binary (any use)
Used ≥1 conventional oral prevention agent during pre-index	Baseline characteristic	Calculated	Binary (any use)
Used ≥1 of any prevention agent during pre-index	Baseline characteristic	Calculated. Includes the above variable + anti-CGRP mabs + onabotulinumtoxinA	Binary (any use)
	Comorl	oid conditions	
Elixhauser comorbidities	Baseline characteristic	Medical claims	Binary
Elixhauser weighted index	Baseline characteristic	Calculated	Discrete
Elixhauser index categories	Baseline characteristic	Calculated	Categorical: 0, 1, 2-3, 4-5, ≥6
Other chronic pain	Baseline characteristic	Medical claims	Binary (ICD-10)
Chronic migraine	Baseline characteristic	Medical claims	Binary (ICD-10)
Any chronic pain (includes chronic migraine + other chronic pain)	Baseline characteristic	Calculated	Binary

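### The fixed adjustment for pre-index preventive use cannot account for preventive treatment newly started with or after rimegepant, and no other planned analysis does so

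*Protocol*

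**What the plan says.** Protocol section 8.7.1, item 4, states the purpose of the models: "In order to determine the association between rimegepant initiation and reduction of other acute treatments". The exposure is a binary time indicator, 0 before index and 1 after it, in a generalized linear mixed model for fills, quantity, average dose and duration. Discontinuation has its own logistic model, because it is observed once.

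The covariates are all pre-index characteristics, and the list ends with "pre-index use of any prevention agent". Table 1 in section 8.3 defines the preventive variable, "Used ≥1 of any prevention agent during pre-index", as binary any use. The table lists no preventive variable for the post-index period.

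The other relevant provisions are:
- Section 8.2.1 requires equal observation on both sides of index: "Have ≥180 days of continuous enrollment in commercial health plans with both medical and pharmacy benefits prior to and following the index date".
- Section 8.2.2 excludes one kind of migraine co-treatment: "Prior use of other novel agents for acute treatment of migraine (i.e., ubrogepant or lasmiditan) in the pre-index period". Its only other criterion is cancer.
- Subgroup #1 is selected on pre-index use: "Identify all individuals from the total cohort with use of ≥ 1 prevention agent during the pre-index period".
- Sensitivity analysis #1 lengthens both windows to 360 days. Sensitivity analysis #2 removes patients with major surgery or injury.
- Sections 8.1 and 8.9 say that the design cannot establish causation.

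**The concern.** A before/after comparison within persons removes everything about a patient that stays constant. It is exposed to anything else that changes at the same time. A new preventive begun at or after the visit that brings rimegepant is such a change, and one that could lower acute medication use. The covariate list looks as if it deals with prevention, but it records only whether a preventive was used before index.

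The plan recognises the general issue elsewhere. It restricts the index fill to 8 tablets to separate acute from preventive use of rimegepant itself, and it checks robustness to surgery and injury, which can also move opioid fills. Other preventives begun at or after index get no such check. What is at stake is how far a reader can connect a fall in opioid or barbiturate fills with rimegepant initiation, which is the association item 4 sets out to estimate.

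**Working it through.** The protocol gives no effect size, power or preventive start rate, so it has no figure to reproduce. The check has four steps.

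**1. Why the covariate drops out.** For patient i in period t, with log link and random intercept u_i, the model is

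log(mean) = b0 + u_i + b1 × post_t + g × P_i + other fixed baseline terms,

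where P_i is pre-index preventive use. Within a patient, post minus pre is b1 + (g × P_i - g × P_i) = b1. With 180 days on each side for everyone, the estimate of b1 does not depend on whether P_i is in the model.

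**2. Size, by arithmetic.** Assume rimegepant has no effect. A share s starts a preventive, which lowers their fills by r over a fraction c of post-index time. Assume starters have the same prior fill rate as others and that nobody stops a preventive. The apparent change is -(s × r × c). All inputs are assumptions:
- s = 0.10, r = 0.20, c = 1: 2 percentage points.
- s = 0.30, r = 0.20, c = 1: 6 percentage points.
- Wider range: 0.10 × 0.20 × 0.5 = 1 point, up to 0.40 × 0.50 × 1 = 20 points.

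If a share q stops a preventive and their fills rise by the proportion r' over a fraction c', the net change is -(s × r × c) + (q × r' × c'). This can be zero or positive.

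**3. Check by simulation.** One data set was generated with 3,000 patients, 6 + 6 windows and a true rimegepant rate ratio of 1.00. About half were pre-index preventive users, with a fill rate exp(0.3) = 1.35 times that of non-users. A preventive was started at index by 35% of non-users and 15% of users, cutting fills by 40%. The rate-weighted share starting is (0.35 × 1 + 0.15 × 1.35) / (1 + 1.35) = 0.235, so the expected spurious ratio is 1 - 0.235 × 0.40 = 0.906.

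| Analysis | Post/pre rate ratio (95% CI) |
|---|---|
| Unadjusted, Poisson GEE | 0.9245 (0.900 to 0.949) |
| Adjusted for pre-index preventive use and age | 0.9245 (0.900 to 0.949) |
| Pre-index preventive users only (as in subgroup #1) | 0.963 (0.930 to 0.996) |
| Time-varying new-preventive term added | 1.012 (0.984 to 1.041) |
| Patients starting a preventive excluded | 1.012 (0.984 to 1.041) |

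A random-intercept Poisson model gave the same post coefficient, -0.0785, with and without adjustment. A linear mixed model gave -0.307 fills per 180 days in both fits. All starts took effect at index, so the exclusion row speaks to co-initiation only. Starts later in follow-up, or in the 30 days before index, were not simulated.

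**4. Does anything else in the plan catch it?**
- The exclusion of ubrogepant and lasmiditan concerns acute drugs before index.
- Subgroup #1 requires a pre-index preventive but does not restrict later additions or switches.
- Neither sensitivity analysis refers to preventives.
- Alprazolam, rescue inhalers and statins serve as comparators for continuous or episodic use. A fall in migraine-driven opioid or butalbital fills after a new preventive would not be expected to show in them.

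**The case against.** The strongest reply is that the protocol claims no cause. The primary objective is to evaluate changes after initiation, item 4 speaks of association, section 8.1 says the design cannot establish causation, and section 8.9 says findings cannot be attributed to a specific cause. This is fair, and it rules out one tempting inference, that the plan credits rimegepant with the whole decline in co-treated patients. It does not. But these caveats are generic. They do not name concurrent preventive starts or let a reader gauge how common they were.

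Other objections limit the point:
- A reader might infer that subgroup #1 makes matters worse, because one recent preventive fill qualifies. The documents do not show that. The subgroup drops patients with no pre-index preventive use, and hence their first starts. In the simulation its bias was smaller, though that rests on the assumed start rates and recent pre-index starters were not modelled. The supported statement is that the subgroup does not resolve the problem.
- A bias towards reduction is not certain. No passage says how often preventives are started or stopped around index.
- The within-person argument does not describe the discontinuation model, which has no pre/post contrast.
- An exclusion from day -30 to index covers co-initiation only. Handling later starts means conditioning on treatment that may itself depend on the course under rimegepant.

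The matter cannot be treated as left to another document: section 8.7 refers to the statistical analysis plan set out in 8.7.1, and that section fixes the covariates.

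**Conclusion.** The point holds for the mixed models of fills, quantity, dose and duration. A fixed pre-index indicator, used as a main effect in balanced data, cannot account for preventives newly started with or after rimegepant, and nothing else in the plan does.

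The consequence is conditional. If starts outnumber stops around index and preventives lower opioid or barbiturate fills, the association is biased towards reduction. The illustrative 2 to 6 percentage points assume 10% to 30% starting, 20% fewer fills over the whole post-index period and no offsetting stops. The documents do not support a conclusion that an observed decline is spurious, or that the bias has a known size or direction. The point calls for an inexpensive improvement and does not overturn the design.

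**What to change.** - **Describe.** For each medication group, report the share whose earliest fill or medical claim for a preventive class falls from day -30 to day +180, and the share stopping one. State how far back within the pre-index period a class must be unclaimed for a start to count as new.
- **Sensitivity analysis for co-initiation.** Repeat the fill, quantity, dose and duration models excluding patients whose earliest fill or medical claim for a preventive class falls from day -30 to the index date inclusive. This uses no post-index information.
- **Supplementary model for later starts.** Fit the model on the 30-day windows W1 to W12 with a time-varying new-preventive indicator, labelled as conditioning on post-index treatment. Specify the windows, because section 8.7.1 does not settle whether the mixed models use the windows or the two aggregates.
- **Limitation.** Name concurrent preventive starts in section 8.9.
- Leave subgroup #1 as defined, since it serves the secondary objective on preventive users.

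The cost is one table, two analyses and a sentence, using preventive classes already in Table 1. The sensitivity analysis will have a smaller sample. Some exclusions will reflect drugs such as beta blockers or antidepressants started for other conditions. The abstract says analyses were completed in 2024, so the additions must be labelled post hoc. The final study report is scheduled for 01 March 2026.

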8.4. Data Sources

This study will use the IQVIA PharMetrics® Plus longitudinal health plan database with medical and pharmacy claims adjudicated by third-party payers managing commercial health plans. Individuals in this database are a geographically representative sample of the US commercially insured population⁴⁰. The database contains information on patient demographics, plan enrollment, inpatient and outpatient medical claims, and outpatient pharmacy claims. These data were used as presented by the data source, without recoding. The primary outcomes in this study are based on observed pharmacy fills for the medications of interest (opioids, barbiturates, alprazolam, rescue inhalers, or statins) for any reason, so minimal interpretation or reliance on clinical coding accuracy is required. The data are de-identified and compliant with the Health Insurance Portability and Accountability Act (HIPPA)⁴⁰. This data source has been used extensively in pharmacoepidemiology research⁴⁵⁻⁴⁹.

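### The surgery/injury check is barred from the problematic-opioid-use subgroup, and no analysis shows opioid change by other chronic pain, although outcomes count opioid fills for any indication

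*Protocol*

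**What the plan says.** Section 8.4 states that the primary outcomes are observed fills of the study drugs "for any reason, so minimal interpretation or reliance on clinical coding accuracy is required". Section 8.7.1 step 4 introduces the models for the same fills with a narrower label: "In order to determine the association between rimegepant initiation and reduction of other acute treatments". The exposure in those models is a within-person pre/post period indicator. One of the adjustment covariates is "presence of any chronic pain (migraine or non-migraine". Table 1 (Section 8.3) shows this to be a composite of two variables that it also lists separately, 'Chronic migraine' and 'Other chronic pain'.

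Step 5 defines the problematic-use subgroup within the opioid group by either of two criteria. For the first, "The first method will identify individuals in the cohort with ≥ 3 opioid prescriptions during the pre-index period". The second is membership of the top quartile of pre-index MME. Neither criterion refers to indication. Sensitivity analysis #2 is to "Exclude all patients having a major surgical procedure or injury diagnosis at any point during the study period". Step 5 limits where it is run: "The sensitivity analyses only apply to the total cohort, and not the additional subgroups".

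**The concern.** The subgroup is chosen because pre-index opioid volume is high, and the outcome is whether that volume falls. Some of it may be postoperative or post-injury analgesia that stops when the pain resolves, whatever is prescribed for migraine. Patients who qualify on such a course will show a fall that a reader of the objective 4 results would naturally associate with rimegepant. The control drugs do not guard against this: alprazolam, rescue inhalers and statins are not analgesics and cannot show an analgesic course ending.

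The plan recognises the issue, since sensitivity analysis #2 exists to test robustness to it. It then withholds that check from an analysis selected on high opioid volume, by an explicit rule and not by leaving a detail open.

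A related gap is that opioid use for another chronic pain condition may be fairly stable over the year. Pooled results then mix patients in whom change is more and less likely. Table 1 already holds the variable needed to show this, but no model, stratum or subgroup uses it on its own.

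**Working it through.** The plan states no figure to reproduce here: Section 8.5 gives no power calculation or effect size, and no section gives opioid use by reason. The inputs below are assumptions, chosen only to show direction and rough scale.

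**1. Courses that end, in the problematic-use subgroup.** Let *s* be the share of pre-index MME from surgical or injury courses that end, with all other use unchanged and no new courses after index. The apparent fall equals *s*:
- *s* = 10%: fall 10%
- *s* = 30%: fall 30%

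New courses after index would offset part of this, so these are upper values for each *s*. The calculation restates its assumption; it shows what share would matter, not what share exists.

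**2. Dilution in the pooled opioid group.** Pooled fall = migraine share × fall in that part. With a 40% fall in the migraine part:
- share 20%: 0.2 × 40% = 8%
- share 60%: 0.6 × 40% = 24%

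This acts in the opposite direction to item 1.

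**3. What a pooled change can and cannot tell.** If half of fills are for migraine, a 30% fall in those alone gives 0.5 × 30% = 15%. A 30% fall in the other half alone also gives 0.5 × 30% = 15%. The pooled figure does not distinguish the two.

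**4. Illustrative simulation.** Assumptions: 4,000 simulated patients; migraine-related fills fall 30%; other-pain fills unchanged; 25% have surgery or injury, adding on average 1.0 fill before index and 0.2 after; at least one pre-index fill required. Post/pre rate ratios:

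| Analysis | Rate ratio |
|---|---|
| All, merged pain covariate | 0.651 |
| All, two pain variables as main effects | 0.651 |
| All, no pain covariate | 0.651 |
| Without other chronic pain | 0.522 |
| With other chronic pain | 0.735 |
| All, surgery/injury excluded | 0.690 |
| 3 or more pre-index fills | 0.549 |
| 3 or more pre-index fills, surgery/injury excluded | 0.573 |

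Three things follow.
- Splitting the composite as main effects changes nothing. A time-fixed covariate takes the same value in a patient's pre and post records, so it does not move the pre/post contrast. A linear mixed model agreed (-0.935 either way).
- Stratifying by other chronic pain does separate patients. Part of the gap comes from the entry rule. From the assumed means without that rule, the ratios are 1.038/1.568 = 0.662 without other chronic pain and 2.127/2.657 = 0.801 with it. The ordering is the same and the gap is smaller.
- The surgery/injury exclusion moves the subgroup estimate by 0.573 - 0.549 = 0.024, and the total cohort by 0.690 - 0.651 = 0.039. The simulation used only the fill-count criterion; the MME criterion was not examined.

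**The case against.** The strongest reply is that the objectives in Section 7 are descriptive. They ask how opioid and barbiturate utilization changes after initiation, and any-reason fills answer that as written. Section 8.9 discloses that the data do not show why a drug was prescribed (limitation 8) and that findings cannot be attributed to a specific cause (limitation 10). Confining sensitivity analyses to the total cohort is a common choice, and there sensitivity analysis #2 already serves the primary objective. All of this stands, and it limits the point. It does not explain why a check the plan already defines should be withheld from the objective 4 subgroup, and the label in step 4 still claims more than limitation 8 allows.

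A reader might also infer four stronger things that the documents do not support.
- *That merging the pain variables biases the pre/post estimate.* It does not, as shown above. The gap is the missing stratum or interaction.
- *That these two rules are why migraine and non-migraine opioid use cannot be separated.* The main cause is that pharmacy claims carry no indication. Section 6 adds that opioids prescribed for other pain may be taken for migraine, so rimegepant could displace those too. Stratifying by other chronic pain would not isolate migraine use.
- *That one surgical course qualifies patients for this subgroup especially easily.* No passage shows it, and a requirement of three prescriptions in 180 days works against a single short course. In the simulation the exclusion moved the subgroup less than the total cohort.
- *That sensitivity analysis #2 excludes for events anywhere in the calendar data window.* Its term for the period is not defined there, and Section 8.2 uses study months for the patient's own twelve 30-day windows. Either reading is open, and no bias has been shown from either.

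**Conclusion.** The point holds in a limited form and is worth acting on. The problematic-use subgroup is selected on opioid volume of any indication, an opioid course that ends can look like a post-rimegepant fall, and the plan's only check on this is expressly not run there. Separately, the plan never shows opioid change by other chronic pain, although the variable exists.

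The size is unknown. The 10-30% range depends wholly on the assumed share of pre-index MME from courses that end. Under the simulation's assumptions the exclusion had a modest effect on the fill-count subgroup (0.549 to 0.573), while stratification made a larger difference (0.522 against 0.735, part of it due to the entry rule). The primary objective is less exposed, because sensitivity analysis #2 already covers the total cohort. After the changes below, residual mixing of indications would remain and would still have to be stated as a limitation.

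**What to change.** 1. In Section 8.7.1 step 5, amend the scope rule so that sensitivity analysis #2 is also run in the problematic-use subgroup.
2. In step 4, report opioid change with and without 'Other chronic pain', using a period-by-other-chronic-pain interaction. Splitting the composite into two main effects is not a substitute. The discontinuation model has no period term, so there report the proportion discontinuing in each stratum.
3. In step 4, describe the outcome as opioid and barbiturate fills for any indication, in line with Section 8.4 and limitation 8.

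The abstract says the analyses were completed in 2024, and Section 5 plans the final report for 01 March 2026. Items 1 and 2 should therefore be labelled in that report as additional analyses. They use variables and an exclusion the protocol already defines. The cost is a few more model runs and table columns, and wider intervals in the smaller strata.
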